#### 8.6. GC4419/Placebo Administration

GC4419 or Placebo/saline mixture will be administered intravenously at an infusion rate that totals 60 min (± 6 min to account for saline overfill) for the total dose assigned. Infusions of GC4419/Placebo must be administered using an infusion pump (i.e., not by drip rate). Infusion pump models are not specified and may be per institutional preference/standard. If sterile 0.2 or 0.22 micron syringe filters are not used during infusion preparation, 0.2 or 0.22 micron inline filters must be used during IV administration.

To facilitate administration of GC4419/Placebo according to the study schedule, an indwelling venous access device may be used, at the discretion of the treating Investigator.

IMRT must be initiated as soon as possible upon completion of the GC4419/Placebo infusion, but no later than 60 minutes following the end of the infusion.

GC4419/Placebo will be given beginning on the first day of radiation and continuing daily, concurrent with each dose of IMRT, to a cumulative radiation dose of approximately 60-72 Gy.

Table 3 outlines the chemoradiation and GC4419/Placebo administration schedules. Please note chemotherapy is not required to be administered on the study days listed in Table 3 as long as it follows a weekly or tri-weekly schedule.

If IMRT is not administered on any given day due to a treatment break or unforeseen circumstances, GC4419/Placebo should not be administered on that day. Breaks in IMRT will be determined by the subject's treating physician in accordance with standard of care. Subjects should resume GC4419/Placebo administration when IMRT resumes. On days when planned doses of both GC4419/Placebo and IMRT are not administered (e.g., due to a holiday site closure), GC4419/Placebo dosing may be extended along with IMRT to make up the missed dose(s) to a maximum of 35 doses of GC4419/Placebo. If a fraction of IMRT is not administered for any reason after GC4419/Placebo has been administered, that day's GC4419/Placebo will count as one of the 35 doses.

Table 3: Chemoradiation and GC4419/Placebo Administration Schedule Example: 35 Doses of GC4419/Placebo (5 days/week over 7 Week Schedule)

Treatment	Week 1				Week 2				Week 3				Week 4							
	Day	Day	Day	Day	Day	Day	Day	Day												
	1	2	3	4	5	8	9	10	11	12	15	16	17	18	19	22	23	24	25	26
GC4419/Placebo 	X	X	X	X	X	X	X	X	X	X	X	X	X	X	X	X	X	X	X	X
Cisplatin 																				
Tri-Weekly	X															X				
Weekly	X					X					X					X				
Radiation 	X	X	X	X	X	X	X	X	X	X	X	X	X	X	X	X	X	X	X	X

Galera Therapeutics, Inc.

Treatment	Week 5				Week 6					Week 7					
	Day	Day	Day	Day	Day	Day	Day	Day	Day	Day	Day	Day	Day	Day	Day
	29	30	31	32	33	36	37	38	39	40	43	44	45	46	47
GC4419/Placebo 	X	X	X	X	X	X	X	X	X	X	X	X	X	X	X
Cisplatin  Tri-Weekly											X				
Weekly	X					X					$X^4$				
Radiation 	X	X	X	X	X	X	X	X	X	X	X	X	X	X	X

¹ Intravenous GC4419/Placebo is administered by a 60-minute intravenous infusion (±6 min) once a day for the first 35 days of IMRT (Monday through Friday). IMRT must be initiated as soon as possible upon completion of GC4419/Placebo infusion, but no later than 60 minutes post GC4419/Placebo infusion. On Day 1/Baseline, chemotherapy prehydration and infusion should be administered after GC4419/Placebo infusion and IMRT, if possible. If IMRT is not received on any given day due to a treatment break or unforeseen circumstances, GC4419/Placebo should not be administered on that day. Subjects should resume GC4419/Placebo administration when IMRT resumes. If a subject is scheduled to receive IMRT on a weekend day (e.g., to make-up for a holiday site closure), the Investigator should contact the Medical Monitor for a discussion prior to IMRT administration.

<sup>2 Cisplatin monotherapy should be administered in a standard q3 weeks regimen (100 mg/m^2) or weekly regimen (40 mg/m^2). Anti-emetic prophylaxis and hematopoietic growth factor use should be administered per ASCO guidelines. If institutional guidelines permit, cisplatin may be administered prior to or after the first day of IMRT. On days in which chemotherapy and GC4419/Placebo are administered, the administration sequence should be GC4419/Placebo, IMRT, prehydration, and then cisplatin, if possible. Patients treated with induction chemotherapy prior to concomitant chemoradiation are not eligible for this study.

Clinical Study Protocol GTI-4419-301 Confidential

 Eligible patients will be scheduled to receive a continuous course IMRT delivered in single daily fractions of 2.0 to 2.2 Gy, five days per week (Monday through Friday), with a cumulative radiation dose of 60-72 Gy. Planned radiation treatment fields must include at least two oral sites (buccal mucosa, floor of mouth, tongue, soft palate) that are each planned to receive  $\geq$  50 cumulative Gy.

Galera Therapeutics, Inc.

<sup>4 The 7th dose of cisplatin will only be administered if the subject is on the 7-dose weekly cisplatin schedule (weekly cisplatin schedule may be 6 or 7 doses, depending on Investigator choice).

# 8.7. GC4419/Placebo Accountability and Compliance

Compliance with GC4419/Placebo dosing, including administration details (e.g., volume, start, stop times, etc.) should be documented in the source documents and recorded on the CRF.

Galera Therapeutics, Inc.

Version: Amendment 4

The Investigator is responsible for ensuring adequate accountability of all used and unused GC4419/Placebo. This includes acknowledgment of receipt of each shipment of GC4419/Placebo (quantity and condition), subject dispensing records, and quantity of GC4419/Placebo returned or destroyed. Dispensing records will document quantities received from the Sponsor and quantities dispensed to subjects, including container number or lot number, date dispensed, subject identifier number, subject initials, and the initials of the person dispensing the medication. Any GC4419/Placebo that is prepared but not used must also be recorded in the dispensing records.

All GC4419/Placebo supplies and associated documentation will be reviewed and verified by the study monitor. All GC4419/Placebo and used containers are to be retained by the site until notified by the study monitor, who will instruct the site in the disposal and/or destruction of all used GC4419/Placebo supplies. Copies of all forms, documenting drug receipt at the study site, drug transportation to satellite sites, and drug return to the Sponsor, together with drug accountability records, will be retained according to the regulations governing record retention.

The Investigator will not allow GC4419/Placebo to be given to any patient not included in the study or to any unauthorized person.

# 8.8. GC4419/Placebo Handling and Disposal

After completion of the study, all unused GC4419/Placebo will be inventoried and, if possible, destroyed locally at the site. GC4419/Placebo should not be returned directly to the Sponsor unless specifically requested by the Sponsor. The study monitor will instruct the site in the disposal and/or destruction of all used and unused GC4419/Placebo supplies. Destruction of any GC4419/Placebo should be documented appropriately.

## **8.9.** Concomitant Medications

All concomitant therapies (i.e., prescription and over-the-counter medications) taken by subjects from the date of randomization through 30 days following the last GC4419/Placebo, IMRT or cisplatin (i.e., whichever occurs last) dose will be collected in the CRF. Additionally, any concomitant therapies if used to treat any serious or related adverse event will be recorded in the CRF.

Anti-emetic prophylaxis and hematopoietic growth factors should be used per ASCO guidelines (Hesketh, Kris et al. 2017).

Subjects who withdraw consent for GC4419/Placebo should be encouraged to continue and complete standard IMRT/cisplatin treatment and other protocol procedures, notably scheduled OM assessments

However, if a subject withdraws consent for the study or is removed from the study completely (i.e., the subject is no longer participating in any study procedures or follow-up) no further data should be collected after the date of the subject's study discontinuation.

#### **8.9.1.** Prohibited Medications

Investigators may prescribe any concomitant medication or supportive therapy deemed necessary to provide adequate supportive care including antiemetics, systemic antibiotics, hydration to prevent renal damage, topical fluoride etc., with the following exceptions:

Galera Therapeutics, Inc.

Version: Amendment 4

Low-level laser treatment for OM

Amifostine (Ethyol®)

Benzydamine (Difflam®, Pharixia®, Tantum Verde)

Cetuximab (Erbitux®)

Glutamine in any form

GM-CSF applied topically

'Magic mouthwashes' or 'Miracle mouthwashes' are permitted, provided they do not contain:

- Chlorhexidine
- Hydrogen peroxide
- Diphenhydramine (Benadryl®) liquid formulation
- Tetracycline
- Any other listed disallowed medications
- Notes:
  - Topical lidocaine preparations are permitted
  - o Diphenhydramine (Benadryl®) administered as tablets or by injection is permitted

MuGardTM, Gelclair®, Episil®, or other barrier devices

Caphosol®

Nitrates, phosphodiesterase type 5 (PDE 5) inhibitors (e.g., sildenafil, tadalafil, or similar agents) or other drugs that in the judgment of the treating Investigator could create a risk of a precipitous decrease in blood pressure are prohibited until at least 24 hours after the last dose of GC4419

Pyridostigmine or other drugs that in the judgment of the treating Investigator could create a risk of increased carotid sinus sensitivity, symptomatic bradycardia, or syncopal episodes are prohibited until at least 24 hours after the last dose of GC4419

Palifermin (Kepivance®) or other keratinocyte or fibroblast growth factor

Povidone-iodine rinses

Steroid rinses

Sucralfate in suspension form (use of sucralfate tablets is permitted)

Other biologic response modifiers – except systemic hematopoietic growth factors for the management of anemia or myelosuppression

Galera Therapeutics, Inc.

Version: Amendment 4

Concurrent approved or investigational anti-cancer therapy (e.g., chemotherapy, immunotherapy, targeted therapy, hormone and biologic therapy) other than the Protocol regimen

Other investigational agents or perceived herbal/homeopathic or other remedies for OM, which are considered investigational for purposes of this study (includes nitric oxide)

# All medication restrictions begin on Day 1 of IMRT and GC4419/Placebo. All medication restrictions end after post-IMRT OM follow-up is completed unless otherwise noted.

Subjects who receive prohibited medications prior to completion of post-IMRT OM follow-up will not automatically be removed from the study; however, administration of a prohibited medication is a significant deviation from the protocol and must be reported to the Medical Monitor as soon as possible and the presiding IRB/IEC/REB (per institutional guidelines). The decision for study continuation or discontinuation will be made at that time on a case-by-case basis and in consideration of the clinical requirement and circumstances.

Although unlikely to affect OM, diphenhydramine (Benadryl®) should not be used in mouthwashes or rinses.

Chlorhexidine oral rinse may exacerbate OM and should not be used.

Mouthwashes or rinses containing sodium bicarbonate, clotrimazole (Mycelex), nystatin, fluconazole (Diflucan), viscous xylocaine, and/or viscous lidocaine are permitted. If a subject uses "Magic Mouthwashes" or "Miracle Mouthwashes," all ingredients must be recorded in the subject's medical record in order to confirm the mouthwashes did not contain the prohibited ingredients listed above.

Anti-emetic prophylaxis and hematopoietic growth factor use are permitted per ASCO guidelines. Following ASCO (and MASCC) guidelines for the prevention and management of chemotherapy-induced nausea and vomiting (CINV) is strongly encouraged.

Oral care per International Society of Oral Oncology (ISOO) guidelines is strongly recommended for all subjects as part of standard of care (Appendix 6).

#### 8.9.2. CYP2D6 Substrates

In vitro, GC4419 inhibited cytochrome P450 isozyme 2D6 (CYP2D6) with an IC50 of 0.079  $\mu$ M. Other cytochrome P450 isozymes were not inhibited in vitro. This prompted a clinical drugdrug interaction study in healthy human subjects, which demonstrated that GC4419 is a strong inhibitor of CYP2D6.

Concomitant use of GC4419 increases the concentration of drugs that are CYP2D6 substrates, which may increase the risk of toxicities of these drugs. Concomitant use of GC4419 with CYP2D6 substrates with a narrow therapeutic range should be considered carefully (CYP2D6 substrates where minimal increases in concentration of the substrate may lead to serious or life-threatening toxicities). Such CYP2D6 substrates include certain beta blockers (e.g., propranolol and metoprolol), antidepressants (e.g., tricyclics), antipsychotics (e.g., phenothiazines and most atypicals), and antiarrhythmics (e.g., propafenone, flecainide) (see Appendix 7 for additional examples).

In addition, concomitant use of GC4419 may decrease the concentration of active metabolites of prodrugs that require CYP2D6 for activation. Concomitant use of GC4419 with CYP2D6 prodrug substrates requiring functional CYP2D6 activity for their clinical benefit (e.g., codeine, tramadol, taxomifen) may decrease their effectiveness.

Galera Therapeutics, Inc.

Version: Amendment 4

Concomitant administration of a CYP2D6-substrate drug concurrent with administration of GC4419 should be limited to cases in which the treating investigator has determined that the use of the specific CYP2D6-substrate drug is medically necessary. In such cases, the patient should be carefully observed for clinical adverse events of the CYP2D6-substrate drug, the dose of which may require reduction.

# 9. TOXICITY MANAGEMENT

# 9.1. Dose Delays and Dose Modifications for Toxicity

The following toxicity requires a 25% dose reduction in GC4419/Placebo:

Grade 2 or greater hypotension within 2 hours after the start of GC4419/Placebo infusion (i.e., anytime from start of infusion through 1 hour after end of infusion).

The dose of GC4419 or Placebo may be reduced by 25% for Grade 3-4 adverse events (AEs) judged by the Investigator to be likely attributable to the study infusion.

Two dose reductions for toxicity will be permitted per subject. After the first event, the subject will be re-challenged at 75% of the original dose (7.5 mL GC4419/Placebo in 250 mL normal saline). After the second event, the subject will be re-challenged at 50% of the original dose (5.0 mL GC4419/Placebo in 250 mL normal saline). Subjects who are unable to tolerate GC4419/Placebo infusions following 2 dose reductions must be discontinued from the study treatment but should continue with cisplatin/IMRT and other study assessments and procedures, with the concurrence of the treating Investigator, if the subject maintains informed consent to do so.

For other toxicities (including those attributable to cisplatin and IMRT), management will be per institutional and ASCO guidelines and Investigator judgment.

The Sponsor strongly recommends managing treatment modifications for cisplatin related toxicities by reducing the dose and/or altering the schedule of cisplatin administration. Such modifications may be made per the judgment of the treating Investigator. However, substitution of other systemic agents (e.g., carboplatin with or without paclitaxel, cetuximab, etc.) is not consistent with the protocol and should not be done.

OM will not be considered an AE requiring dose modification for the purposes of this study.

# 9.2. Supportive Care Guidelines

Necessary supportive measures for optimal medical care will be given throughout the study. Supportive care medications may be administered at the Investigator's discretion and recorded in the CRF (including administration of prophylactic antiemetic medication if deemed appropriate by the Investigator). However, medications are subject to the exclusions listed in Section 8.9.1.

# 9.2.1. Supportive care for chemotherapy-induced nausea and vomiting (CINV)

Medication to prevent or manage chemotherapy-induced nausea and vomiting (CINV) should follow recent guidelines from ASCO and MASCC (Appendix 5). Adult patients who are treated with cisplatin (considered a high-emetic-risk single agent for the purposes of these guidelines) should be offered a four-drug combination of a NK1 receptor antagonist, a serotonin (5-HT3) receptor antagonist, dexamethasone, and olanzapine. Dexamethasone and olanzapine should be continued on days 2 to 4. (Type: evidence based, benefits outweigh harms; quality of evidence: high; strength of recommendation: strong.) (Hesketh, Kris et al. 2017).

Galera Therapeutics, Inc.

Version: Amendment 4

Supportive care for CINV should be optimized, per ASCO and MASCC guidelines, before GC4419 dose is reduced for nausea and vomiting.

## 10. ASSESSMENTS

The study procedures to be conducted for each subject enrolled in the study are described in the text that follows and presented in the Schedule of Assessments in Appendix 1.

Any deviation from protocol procedures should be explained in the source documents. The Sponsor (or designee) and the site's institutional review board (IRB) – as required by the IRB's policies and procedures – should be notified as soon as possible of any deviations potentially affecting subject safety, GC4419/Placebo administration or the assessment of safety, efficacy and tolerability parameters.

## 10.1. Safety Assessments

Safety will be assessed on the basis of treatment-emergent AEs, physical examination findings, clinical laboratory tests, electrocardiogram (ECG) measurements, and vital sign measurements.

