- 16. Medical history that includes any condition, or requires the use of concomitant medications which, in the Investigator's judgment, are associated with or create a risk of increased carotid sinus sensitivity, symptomatic bradycardia, or syncopal episodes.

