#### 10.1.1. Clinical Assessments

The following clinical assessments are defined when referenced in the schedule of events for this study:

12-Lead ECG: ventricular rate, P-R interval, QRS interval, QT interval, and QTc

Vital signs: measured following two minutes of rest in the sitting position – temperature, systolic and diastolic blood pressures, heart rate and respiration rate

Weight and Height: measured in kilograms (kg) and centimeters (cm), respectively

Performance Status: ECOG (see Appendix 3 for conversion criteria for Karnofsky to ECOG)

Vital signs are required to be taken at Screening, Day 1 (Baseline), once during Week 4, once during Week 7 and any additional IMRT weeks, and on the Last Day of IMRT. On Day 1 (Baseline) and Day 22, blood pressure must be measured at the following times:

- 1. Within 30 minutes prior to the pre-GC4419/Placebo PK draw, and
- 2. After GC4419/Placebo infusion, prior to standing and prior to the End of GC4419/Placebo Infusion PK draw.

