### 10.8. Screening

The following screening observations and procedures will be completed within 28 days of IMRT and GC4419/Placebo start:

Galera Therapeutics, Inc.

Version: Amendment 4

Obtain a signed IRB/IEC/REB-approved informed consent form (ICF)

Confirm subject eligibility by reviewing inclusion/exclusion criteria

Obtain medical history, tobacco use history, and alcohol use history

Obtain HNC history; HNC history should include:

- Tumor HPV status, and strain(s) if known
- Pre-treatment tumor imaging (See Section 10.6.2.1)
- Prior treatments
- Confirmation of histopathological diagnosis of SCC
- Tumor staging (AJCC 8th Edition) (pre-surgical staging for surgical subjects if available; otherwise, provide post-surgical staging)

Conduct a complete physical examination, including height

Ensure a dental examination was conducted for IMRT clearance and potential sources of mucosal irritation (e.g., tooth extraction) were eliminated. The dental exam must occur within the 28-day screening period. The exam must be performed by a licensed clinician, but not necessarily by a dentist. For edentulous subjects, the subject must be cleared for IMRT per SOC (i.e., oral exam).

Conduct OM assessment and record the WHO score

Record planned IMRT and chemotherapy parameters

Measure vital signs, body weight, and ECOG Performance Status

Conduct a 12-lead ECG

Record concomitant medications from date of randomization

Record AEs from date of randomization

Record/update medical conditions and illnesses that have occurred since the subject signed the ICF and record in medical history

Draw blood for laboratory measurements

- Chemistry profile
- Hematology profile
- Biomarker sample for pro-inflammatory cytokine analysis (See Section 10.5)
- For subjects who consent separately: RNA sample (PAXgene) for genomic studies (See Section 10.5)
- Serum pregnancy test for women of childbearing potential

All questions related to subject eligibility should be directed to Galera's Medical Monitor or designee.

Galera Therapeutics, Inc.

Version: Amendment 4

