- Ventricular rate and P-R, QRS, QT, and QTc intervals will be assessed and recorded at Screening.

Galera Therapeutics, Inc. Version: Amendment 4

- $^{13}$ All OM assessments must be performed by trained evaluators. The extent of the subject's OM will be scored using the WHO OM toxicity scale. OM assessments will be completed at the Screening Visit, at the Baseline Visit, and twice weekly (no less than two days apart) within each 5-day IMRT period. For Week 1, the first OM assessment will occur at the Baseline Visit and one additional OM assessment must occur at least two days later during the week. The extent of the subject's OM will be scored using the WHO OM toxicity scale. All subjects will be seen at  $7 \pm 2$  calendar days from the last day of IMRT and  $14 \pm 2$  calendar days from the last day of IMRT.
- For a woman of childbearing potential, serum pregnancy test must be performed at the Screening Visit.
- Clinical laboratory measurements will be conducted at the Screening Visit, twice during Week 1 (once at the Baseline Visit and again on Day 3, 4 or 5), and once weekly from Week 2 through the last day of IMRT. Clinical laboratory measurements at these visits will include the hematology profile (hemoglobin, hematocrit, red blood cell count, white blood cell count with differential, and platelet count. Differential to include total neutrophils, lymphocytes, monocytes, eosinophils, and basophils) and chemistry profile (glucose, BUN, creatinine, sodium, potassium, calcium, albumin, total protein, total bilirubin, direct bilirubin, alkaline phosphatase, ALT (SGPT), AST (SGOT), chloride, phosphate, bicarbonate, magnesium).
-  If safety labs have already been drawn during the study week in which the last day of IMRT or early termination visit falls, then lab safety tests (chemistry and hematology profiles) do not need to be conducted on the last day of IMRT or at the early termination visit. If safety labs have not been drawn during the current study week at the time of the early termination visit or on the last day of IMRT, then safety labs should be drawn on that day. Safety labs only need to be drawn once per study week after Week 1.
- Blood samples will be collected for serum cotinine test at Baseline (Day 1), once during Week 4, and on the Last Day of IMRT.

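### The ECG that Section 10.1 counts as safety evidence is scheduled only at Screening, and no heart-rate reading is required after any infusion

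*Combined protocol and SAP*

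**What the plan says.** Section 10.1 lists "clinical laboratory tests, electrocardiogram (ECG) measurements, and vital sign measurements" among the bases for assessing safety, with treatment-emergent adverse events and physical examination. Section 10.1.1 defines the ECG as "12-Lead ECG: ventricular rate, P-R interval, QRS interval, QT interval, and QTc", and vital signs as "temperature, systolic and diastolic blood pressures, heart rate and respiration rate".

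The ECG appears once in the visit text, in Section 10.8: "Conduct a 12-lead ECG". Table 6 has a single mark for it, in the Screening column, and footnote 12 reads "Ventricular rate and P-R, QRS, QT, and QTc intervals will be assessed and recorded at Screening". The visit lists in Sections 10.9 and 10.10 contain no ECG.

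Section 10.1.1 requires vital signs at Screening, on Day 1, once in Week 4, once in Week 7 and in any additional IMRT weeks, and on the last day of IMRT. It then adds a separate requirement: "On Day 1 (Baseline) and Day 22, blood pressure must be measured at the following times". The two times are shortly before the pre-infusion PK draw, and after the infusion but before the end-of-infusion PK draw. Sections 10.9.1 and 10.9.6 and Table 6 footnote 6 repeat this, and all name blood pressure only.

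Section 12.4 summarizes laboratory values and vital signs by treatment group at the scheduled time points. It does not mention ECG.

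Exclusion 16 (Section 7.2) concerns conditions and medications that "create a risk of increased carotid sinus sensitivity, symptomatic bradycardia, or syncopal episodes", and Section 8.9.1 prohibits such drugs until at least 24 hours after the last GC4419 dose. Section 8.9.2 reports that GC4419 is a strong CYP2D6 inhibitor that raises concentrations of substrates, among them certain beta blockers and antiarrhythmics.

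**The concern.** Two things do not fit together. First, a single ECG taken before the first dose describes who entered the trial. It cannot show a change on treatment or a difference between arms, so it cannot serve as the safety basis that Section 10.1 makes it.

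Second, the protocol takes haemodynamic effects around the infusion seriously. Section 9.1 ties a dose-modification rule to hypotension within 2 hours of the start of infusion, the post-infusion blood pressure is taken before the subject stands, and drugs and conditions predisposing to bradycardia or syncope are restricted. CYP2D6 substrates are limited to cases of medical necessity rather than prohibited, so any rise in their levels would occur in the active arm only. Yet the one variable that would describe an acute rate effect is not required at the moment when blood pressure is.

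At stake is whether the safety database of a trial intended to support a marketing application can describe heart rate after infusion by arm.

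**Working it through.** This is a count of required measurements. The plan gives no figure of its own to reproduce.

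**ECG.** Section 10.8, the ECG row of Table 6 and footnote 12 agree on one ECG, at Screening. Scheduled ECGs after the first dose: 0.

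**Heart rate.** It is collected only as part of vital signs. Setting the visit lists side by side:

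| Visit | Heart rate (in vital signs) | Named reading after infusion |
|---|---|---|
| Day 1 (10.9.1) | before first dose | blood pressure |
| Week 4 (10.9.6) | once in the week, before dosing | blood pressure, Day 22 only |
| Week 7 and extra IMRT weeks (10.9.9) | once, before IMRT; no timing relative to infusion | none |
| Last day of IMRT (10.9.10) | before dosing | none |

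Table 6 footnote 21 allows up to 35 infusions per subject. Therefore:

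- infusions followed by a required blood pressure: 2 of up to 35 (Days 1 and 22);
- infusions followed by a required heart rate: 0 of up to 35.

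The Week 7 reading may fall between infusion and IMRT, so a post-infusion value is possible, but nothing requires it. On Day 22 even the pre-infusion heart rate is not guaranteed, because the Week 4 vital signs may be taken on another day of that week.

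**What the fix could yield.** Section 12.2 plans about 400 ITT subjects (240 GC4419, 160 placebo). With one pre/post pair on each of two days:

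- ceiling: 2 × 400 = 800 pairs (2 × 240 = 480 on GC4419; 2 × 160 = 320 on placebo);
- if, as an extreme assumption, all of the planned 10% early discontinuations came before Day 22: 400 + 0.90 × 400 = 760 pairs.

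Both figures assume that the change covers every subject. Amendment 4 is dated 13 July 2020 and first enrollment was 3 October 2018, about 21.3 months earlier, out of about 32 planned. That leaves 32 − 21.3 = 10.7 months. Assuming even accrual and a change effective on the date of Amendment 4:

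- over the whole period: 10.7 / 32 = 0.33, and 0.33 × 800 ≈ 270 pairs;
- leaving out about 4.1 months without enrollment (28 April to 30 August 2019): 10.7 / 27.9 = 0.38, and 0.38 × 800 ≈ 310 pairs.

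Actual accrual is not in the documents, so this range is only illustrative. A later change would yield fewer.

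**The case against.** The strongest reply is that the gap is narrow and that the plan has other ways of seeing a problem. Much of this stands.

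- A reader might infer that the trial cannot compare heart rate between arms at all. The documents do not support that. On-treatment heart rate is collected in Week 4, Week 7, any extra IMRT weeks and on the last day of IMRT, and Section 12.4 summarizes it by arm. What is missing is a guaranteed reading after infusion.
- A reader might infer that bradycardia would come to light only if symptomatic. That is also too strong. The adverse-event definition in Section 11.1.1 includes signs, Section 11.4 names vital signs as a source, and Section 11.2.3 takes in clinically significant abnormal assessments, with ECGs as its example. These routes catch what happens to be looked at; they do not produce systematic post-infusion data.
- A reader might infer that the protocol calls bradycardia or syncope a GC4419 effect. It does not. Exclusion 16 and Section 8.9.1 attach those risks to medical history and concomitant drugs. The toxicity for which Section 9.1 mandates a dose reduction is hypotension, which the post-infusion blood pressure addresses.
- Section 8.9.2 asks for careful observation of subjects who must take a CYP2D6 substrate, and the DMC reviews unblinded safety data periodically.
- The Investigator's Brochure and earlier studies may already describe ECG and heart-rate effects. They are not available here, so the documents cannot show that this trial needed on-treatment ECGs, and none is asked for.

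On the ECG alone, the schedule is unambiguous and no site would be misled, so that part is a wording correction. The reply does not change the count of required post-infusion heart rates, which is zero.

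**Conclusion.** The point holds in a limited form. Section 10.1 claims ECG as a basis for safety, but the schedule supports no on-treatment ECG comparison by arm. Separately, scheduled heart rate can be compared between arms, mostly before dosing, but none of up to 35 infusions per subject is followed by a required heart rate. An acute post-infusion rate effect can therefore not be assessed reliably from scheduled data.

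This is a worthwhile, inexpensive improvement. It is not evidence of a safety signal, nor of a failure to monitor a known drug effect. The counts rest on the visit lists and Table 6 as written. Sites may record pulse with the cuff reading anyway, but the protocol does not require it, so its availability by arm cannot be assumed.

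**What to change.** In Sections 10.1.1, 10.9.1 and 10.9.6 and in Table 6 footnote 6, add heart rate to the blood-pressure readings already required before and after infusion on Days 1 and 22. In Section 12.4, add a tabulation by arm of the change in heart rate from before to after infusion on each of the two days. In Section 10.1, state that the scheduled ECG is a screening assessment only, so that the text agrees with Table 6 and Section 12.4.

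The cost is one CRF field per reading, with no added visit, blood draw or staff. The drawback is partial coverage: subjects already past Days 1 and 22 cannot contribute, so the yield falls below the ceiling of about 800 pairs, and the tabulation should state how many subjects in each arm supply it.
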